5.3. Pharmacokinetics Endpoints

A population PK model will be developed for DZD.

The following secondary parameters will be derived for DZD (model-based), for BDQ and main metabolite M2, DLM and main metabolite DM-6705, and for MXF (with NCA):

• Area under the plasma concentration curve from morning dosing to 24 hours (AUC 0-24) on day 14 (WK02)

- The observed maximum concentration (Cmax) on day 14
- · Time to reach Cmax (Tmax) on day 14
- The minimum observed plasma concentration (Cmin) at day 14 (24 hours following the last dose for QD and 12 hours following the last dose for BID)

Analyses may be limited by available budget, which may lead to parameters for certain drugs not being reported.

5.4. Mycobacteriology Identification and Characterization Endpoint

Sputum cultures from various timepoints during the study will be assessed as follows:

- Minimum inhibitory concentrations (MIC) of BDQ, DLM, MXF, DZD of the infecting strain, at baseline and on representative isolate(s) grown at or after WK08, if any.
- · Frequency of acquired mutations in the infecting strain over treatment by whole genome sequencing
- Comparison between bacterial strain causing recurrent disease, and the strain at baseline by whole genome sequencing, to discriminate relapse from re-infection.

These assessments will be performed dependent on the availability of lab capacity and budget, so may not be completed for all possible timepoints.

5.5. Exploratory Endpoints

Exploratory endpoints will be analysed depending on laboratory capacity and budget and may not be tested in all trial's sites equally. Refer to DECODE Protocol for more details.

6. Analysis Populations

The ITT analysis population will be primary for all analyses, apart from safety analyses where the safety population will be primary. The Adequate adherence (AA) population will be secondary.

6.1. Intent-to treat (ITT) population:

The ITT population will consist of all randomized participants in the groups to which they were randomly assigned, and who have taken at least one dose of study treatment.

6.2. Modified Intent-to treat (MITT) population:

The MITT population will be the same with ITT population but exclude participants that withdrew from study medications prior to PK sampling.

6.3. Adequate adherence (AA) population:

The AA population will be the same as the ITT population with the following participants excluded:

· Randomized participants not meeting the eligibility criteria

• Participants having missed one or more doses on 10 or more days of their allocated treatment.

6.4. Safety Population

The safety population will be defined as all participants who received any dose of study medication. This population will also be used for the PK and the exposure-response analysis.

7. Baseline Characteristics and Patient Disposition

7.1. Baseline patient characteristics

Baseline characteristics tables will be produced for both the ITT, AA, and safety analysis populations.

Demographic data will be summarized by dose group and overall. Summary statistics will be calculated by age, race and gender, height, weight, HIV status, body mass index (BMI) and bacterial load in sputum as measured by GeneExpert.

The results of the physical examination and vital signs (including systolic and diastolic blood pressure, heart rate, and body temperature), safety laboratory screening sample, chest radiography (X-ray) and ECG data will be tabulated by dose group.

Baseline characteristics, medical history, and analytical data will be summarized using descriptive statistical methods. Continuous data will be summarized using the median, the range (minimum and maximum value) and IQR. Categorical values will be summarized using frequency counts and percentages.

7.2. Patient recruitment

Total numbers of participants screened and randomized and reasons for participants not being randomized will be tabulated by site.

7.3. Patient withdrawal and follow-up

Timing of withdrawal and lost to follow up will be recorded and tabulated, the number and reasons of losses to follow up over the course of the trial will be summarized by treatment arms. The disposition of the participants who discontinue the treatment by meeting the stopping criteria as described in protocol section 13.10 ("Additional safety considerations: individual patient stopping criteria for Safety") will also be recorded and tabulated.

8. Delpazolid Pharmacokinetic Analysis

A population PK (popPK) model of delpazolid will be developed using nonlinear mixed-effects methodology. The analysis will be carried out and reported according to regulatory guidance documents from FDA and EMA: Population Pharmacokinetics Guidance for Industry and Guidance on Reporting the Results of Population Pharmacokinetic Analyses.^{2,3} The model should serve the following purposes:

- · Describe distributions for random inter-individual variability
- Identify and quantify sources of variability (covariates)
- Explore potential nonlinear kinetics
- · Generate exposure metrics for the exposure-response analysis
- Provide a means to simulate exposures of alternative dosing scenarios and/or other populations

8.1.Software

Data management and post-processing of results will be performed in R,⁴ with help of specialized packages as Xpose. The model will be developed in NONMEM 7.4 or later and parameters will be estimated using the First Order Conditional Estimation method with interaction (FOCE INTER).⁵ If this estimation method turns out to generate unreliable results, alternative methods such as the SAEM method will be explored. Computations will be performed on the high-performance cluster managed by Radboudumc Applied Pharmacometrics. The development process will be documented using the Pirana run record system.⁶

8.2. Data Management

A NONMEM dataset will be generated through reproducible scripting in R. The raw PK data will be supplied from the Clinical Pharmacology lab, Radboudumc, in prespecified format (template to be agreed upon between lab and pharmacometrician before start of analysis). Patient characteristics and information about doses and sampling will be extracted from the main database provided from the responsible CRO (Tecro). Actual dosing and sampling dates and times will be used.

8.2.1. Handling of missing and erroneous data

The information on concentrations reported as below the lower limit of quantification (LLOQ) will be included in the popPK analysis. If dosing date or time is missing, the concentration records post the dose will be excluded. Concentration records with missing date or time will be excluded.

Missing values for a covariate at a particular time point will be replaced with an available measurement at the closest time point. For participants with no covariate information the following will be applied:

- Missing continuous covariates will be replaced with the median value in the population. Body weight would be sex-specific if replaced
- Missing categorical covariates will be replaced by the most common category

If a covariate is missing in more than 15% of the participants, more sophisticated methods will be used to impute the covariate based on regression models between covariates.

All imputed values will be flagged. Description of any missing data and the details related to any potential imputation will be recorded in the popPK model report (see 8.4).

8.2.2. Handling of Outliers

Outliers are defined as data points in the datasets that appear to be outside the norm for that dataset. Potential outliers in the popPK analysis will be identified based on inspection of graphical analysis and the output from initial satisfactory runs. The influence of the omitted data will be evaluated by running the final popPK model with all data and investigate the impact on parameter estimation. The reasons for omitting data will be carefully described in the popPK model report (see 8.4).

8.3. Model Components

The popPK model of delpazolid will be developed in steps, starting with the structural and stochastic models before the covariate model.

8.3.1. Structural model

One-, two- and three- compartmental disposition models will be considered for delpazolid. The absorption of delpazolid will be modeled with a first-order function without or with delay through transit compartments. Non-linear relations between dose and bioavailability will be explored, as well as non-linear clearance in relation to concentration (e.g. Michelis-Menten kinetics).

8.3.2. Stochastic model

The between-patient variability will be described using a log-normal distribution of structural model parameters:

$$P_i = \widetilde{P}(\theta, z_i) \cdot e^{\eta_{Pi}}$$

or as a logit transformed distribution to constrain values between 0 and 1 (e.g. for absolute bioavailability):

$$P_i = \frac{e^{(\varphi + \eta_{Pi})}}{1 + e^{(\varphi + \eta_{Pi})}} \text{ where } \varphi = \log \left(\frac{\widetilde{P}(\theta, z_i)}{1 - \widetilde{P}(\theta, z_i)} \right)$$

 P_i represents the value of the PK parameter P for the ith subject, while $\widetilde{P}(\theta, z_i)$ is the typical population value of parameter P in the structural model given the vector of fixed effects parameters θ and the covariate vector z_i of subject i. η_{F_i} is a normally distributed random effect with mean zero and an estimated variance ω^2 ($\eta_{F_i} \sim N[0, \omega^2]$). η_{F_i} describes the deviation of P_i from and $\widetilde{P}(z_i)$. Other models will be considered if indicated by the data.

Additive (homoscedastic), proportional (heteroscedastic) and combined additive and proportional models will be tested on untransformed or log-transformed data (other transformations may be used if applicable). The combined additive and proportional residual error model for drugx for untransformed data follows:

$$C_{ij} = \hat{C}_{ij} \cdot (1 + \varepsilon_{pij}) + \varepsilon_{aij}$$

 C_{ij} is the j^{th} measured observation of drugx in the *i*th individual

8.3.3. Covariate model

When the basic popPK model is established the covariate model will be developed. Initially, allometric scaled body weight will be applied for all volume terms and all clearance terms. Thereafter, further covariates will be evaluated using a stepwise search based on both statistical significance test and clinical significance i.e. the magnitude of the effect of the covariate on the parameter examined.

Allometric scaled body weight will be applied for all volume terms and all clearance terms as follows:

Typical
$$\frac{CL}{F} = \theta_1 \cdot \left(\frac{WT_i}{70}\right)^{\frac{3}{4}}$$

Typical
$$\frac{V}{F} = \theta_2 \cdot \left(\frac{WT_i}{70}\right)^1$$

 WT_i denotes individual body weight; q_1 and q_2 are the typical oral clearance and volume of distribution, respectively, in a patient weighing 70 kg. Other body size metrics, such as fat-free mass, could be evaluated instead of total bodyweight.

The effect of categorical covariates will be evaluated as exemplified here for the effect of SEX on a particular PK parameter P, where P is the typical value for this parameter:

$$P=\theta_1\times(1+\theta_2\times SEX)$$

SEX is an indicator variable, which is equal to 0 for male and 1 for female. Accordingly, q_1 is the typical estimate of the PK parameter for male participants and q_2 is the fractional increase/decrease in the typical parameter value for females (SEX=1) compared to males. The lower limit of q_2 was set to -1 to restrict the typical value to take on a negative value.

The effects of continuous covariates will be evaluated initially with a linear function as exemplified here for the effect of AGE on a particular PK parameter P, where P is the typical value for this parameter:

$$P=\theta_1*(1+\theta_2\times(AGE-AGE_{median}))$$

AGE_{median} is the observed median AGE, q₁ is the typical estimate of the PK parameter at the median age and q₂ is the fractional change in the parameter different from the median age.

The specific parameters-covariate to minimally be tested in the delpazolid popPK model are listed in Table 2 below. When a relation is found statistically significant further investigation determining potential effect of influential individuals will be conducted and an assessment of scientific plausibility and clinical relevance (i.e. resulting in >20% difference in drug exposure) will be made before final decision on inclusion in the model.

Table 2: Covariate relations to be tested					
Parameter Covariates					
Clearance	Body size metrics, Age, Race, HIV-status				
Volume of distribution	Body size metrics, Sex				
Bioavailability	Sex, Race, HIV-status, Dose				

8.4. Model Selection, evaluation and documentation

Model comparisons will be based on the objective function value (OFV), goodness-of-fit plots, precision in parameter estimates and scientific plausibility. A difference in OFV between two nested models is approximately χ^2 -distributed. A difference in OFV \geq 3.84 and 6.63 (one degree of freedom) is thus significant at the 5% and 1% level, respectively.

The final model will be evaluated according to best practice using primarily visual predictive checks (VPCs) and comparison of individual concentration observations and predictions⁷. The model development process will be documented with a run-record exported from Pirana including all key decision points. The popPK dataset, model development process and final model will be described in the popPK model report.

9. Pharmacokinetic analysis companion TB drugs

Non-compartmental PK analysis will be conducted for all the companion drugs (bedaquiline plus metabolite M2, delamanid and moxifloxacin). The following PK parameters will be estimated for day 14 from each participants' individual plasma concentrations by applying a noncompartmental approach using PK software WinNonlin Phoenix or R packages with the same functionality.

Cmax Maximum observed drug concentration

Cmin Minimum observed drug concentration (not including predose observation)

Tmax Time of the maximum drug concentration (obtained without interpolation)

AUC(0-24H) Area under the drug concentration-time curve calculated using Log linear trapezoidal summation from time zero

to time 24 h post dose

In addition, for moxifloxacin the following parameters will be reported:

Kel Terminal elimination rate constant calculated by linear regression of the terminal linear portion of the log concentration vs. time curve

T½ Elimination half-life calculated as ln(2)/Kel

CL/F Apparent oral clearance [Dose/AUC(0-24H)]

Vd/F Apparent volume of distribution following oral administration [Vd/F = (CL/F)/Kel]

The actual elapsed time will be calculated from actual dosing and sampling times and used in the parameter estimation.

The rate constant of the elimination phase (λ_z) will be calculated by log-linear regression of the terminal portion of the concentration-time profile where there are sufficient data (i.e. at least 3 time points and the correlation coefficients for the terminal slope $[R^2]$ is greater than or equal to 0.9). If these criteria are not fulfilled, λ_z and $t_{1/2}$ will not be reported.

During the derivation of individual subject PK parameters plasma concentrations:

- Any values below the LLOQ that occur before the first quantifiable concentration will be replaced with zero.
- Any values that fall below the LLOQ between 2 measurable values will be treated as missing.

Deviations from this convention may be considered on a case-by-case basis as deemed appropriate. These will be documented fully with the rationale for the deviation.

If the concentrations at x h post dose (all after the last measurable concentration) are below the LLOQ they will be calculated using the formula $Cx = C_{last} *e^{-Kcl^*(x-Tlast)}$, in which Clast is the last measurable concentration and Tlast is the time to reach Clast. These extrapolated concentrations will be used together with other measured concentrations to assess the Area under the drug concentration - time curves using Log linear trapezoidal summation from time zero to time 24 h post dose.

In summary plots of mean concentration-time profiles, statistics will be calculated having set concentrations to missing if either of the following cases is true:

- A concentration has been collected as ND (i.e. not done) or NS (i.e. no sample),
- A deviation in sampling time is of sufficient concern or a concentration has been flagged anomalous. This will be documented
 fully with the rationale for the decision.

Plasma concentrations that are below the lower limit of quantification (<LLOQ) will be set to zero in the computation of mean concentration values.

Descriptive statistics including mean, standard deviation, geometric mean, coefficient of variation, median, minimum and maximum will be computed for each PK parameter by dose group. In addition, mean and median concentration-versus-time graphs will be provided (with error bars as appropriate).

10. Primary Efficacy Analysis: Exposure-response modelling

To establish an exposure-response model for delpazolid, the change in liquid culture MGIT time to positivity (TTP) will be modeled and linked to derived PK metrics. Software and data management will be as described in section 8 (popPK model). The TTP data will be transferred from the responsible CRO (Tecro) in a consistent format. There are two TTP observations from each sampling point and those will be included separately as individual observations (no averaging). In the primary analysis, the MITT analysis population will be used. For patients discontinuing study medications prematurely (before 16 weeks), TTP data collected after the discontinuation will be excluded. Contaminated culture results will be ignored.

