- G) Detailed neurological examination: to include central and peripheral system testing (i.e. cranial nerves testing, vibration sensitivity, position, pin prick, light touch) and vision testing (Snellen, Ishihara). During follow up visits FU 2-4 symptom orientated neurological examination only or to follow up on (S)AEs.
- H) ECG: to be recorded after 10 minutes supine rest, before intake of study treatment. Triplicate ECG at WK00, single ECGs at SCR, WK01 09, WK11, WK13 and WK16. If a QTcF of >480ms, or a QTc-prolongation over baseline of >50ms is seen in a single ECG during experimental treatment, two more ECGs should be registered, to obtain a more precise, average QTcF measurement.
- 1) Microbiology/Susceptibility Testing: rapid test for RIF and INH susceptibility at SCR. Minimum inhibitory concentration (MIC) for study drugs at baseline, and from a representative isolate if any growth at or after WK08.
- J) Screening/Safety lab: full blood count (blood samples of 2mL), ALT, AST, gamma-glutamyl transferase (yGT), Alkaline Phosphatase (AP), Lipase, direct and total bilirubin, albumin, serum creatinine, electrolytes (Na+, K+, Serum Calcium, Magnesium, Cl-, PO4), random glucose (blood samples of 7.5mL for blood chemistry). Urinalysis including dipstick for pH, protein, glucose, ketones, urobilinogen, blood and leukocytes. Urine microscopy on abnormal dipstick results as per the investigator's decision. At SCR and WK02 (and at additional visits, if clinically indicated): Coagulation aPTT, PT, INR (blood samples of 3mL)
- K) Intensive PK sampling (WK02): In all participants, blood samples of 8ml will be taken for measurements of DZD and other study drugs' concentrations over time. Study drugs will be dosed with food. Time of intake of food, drugs and of blood sampling will be recorded. Participants will be hospitalized and receive standard meals at days of intensive PK sampling. Intensive PK time points (7 samples in total) at WK02: 0 (within 1h before dosing), 1, 2, 4, 8, 12, (± 10 mins) and 24 hours (± 30 mins) after dosing

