#### 9.2.3 Pharmacokinetic Endpoints

A population PK model will be developed for DZD. The following secondary parameters will be derived for DZD, for BDQ, DLM and their main metabolites, and for MXF:

- Area under the plasma concentration curve from morning dosing to 24 hours (AUC 0-24) on day 14 (WK02)
- The observed maximum concentration (Cmax) on day 14
- Time to reach Cmax (Tmax) on day 14
- The minimum observed plasma concentration (Cmin) at day 14 (24 hours following the last dose for QD and 12 hours following the last dose for BID)
- Apparent oral clearance (Cl/F)
- Apparent volume of distribution (Vd/F)
- Terminal half-life (t1/2)

Analyses may be limited by available budget, which may lead to parameters for certain drugs not being reported.

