#### Delpazolid

All patients will undergo intensive PK sampling at Day 14 (WK02) visit. A sample will be drawn within 1h before administration of the DZD morning dose (0 h).

The DZD morning dose will be administered with a standardized meal. Blood draws thereafter will be performed at 1, 2, 4, 8, 12 (± 10 mins) and 24 hours (± 30 mins) after DZD morning dose. The exact time of meal and DZD administration at the day of PK sampling will be recorded. Standardized food and fluid intake will be monitored and noted throughout the PK days.

Procedures for sample connection, storage and transportation will be described in the Laboratory Manual. Assaying of DZD, BDQ and DLM plus main metabolites, and MXF will be conducted centrally at the Department of Pharmacy, Radboudumc, the Netherlands, with validated LC-MS/MS methods.

Pharmacokinetic parameters will be assessed using non-compartmental techniques and nonlinear mixed effects methodology. The latter will be utilized to develop a population PK model describing DZD, which will be linked to safety and efficacy parameters. Secondary PK parameters to be reported are listed in section 9.2.3.

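### SAP section 9 takes companion-drug Cmin as the lowest post-dose sample at any time, whereas SAP 5.3 and protocol 9.2.3 tie it to 24 h (once daily) or 12 h (twice daily) after the last dose

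*SAP*

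**What the plan says.** Protocol 9.2.3 lists Cmin on day 14 as a PK endpoint and gives its timing: "at day 14 (24 hours following the last dose for QD and 12 hours following the last dose for BID". SAP 5.3 repeats this and assigns the non-compartmental route: "for BDQ and main metabolite M2, DLM and main metabolite DM-6705, and for MXF (with NCA". Delpazolid is handled separately, from the population PK model.

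SAP section 9, which instructs the analyst who runs the non-compartmental analysis, defines Cmin as "Minimum observed drug concentration (not including predose observation". It excludes the predose value and fixes no time. Its list of analytes is "bedaquiline plus metabolite M2, delamanid and moxifloxacin", so DM-6705, named in SAP 5.3, is absent.

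Sampling is set in note K to the protocol's schedule of events, "Intensive PK time points (7 samples in total) at WK02: 0 (within 1h before dosing), 1, 2, 4, 8, 12" and then 24 h, and in protocol 11.5: "Blood draws thereafter will be performed at 1, 2, 4, 8, 12 (± 10 mins) and 24 hours (± 30 mins) after DZD morning dose".

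**The concern.** The SAP carries two rules for one parameter in the same analytes and does not say which governs. They give different numbers whenever the lowest of the six post-dose values is not the timed trough sample. That is likely where the profile is flat over the day, where absorption is slow enough that the 1 h sample is still near trough, or where the analyte is still rising on day 14 so that early samples lie below the 24 h one. The minimum of several similar noisy values also lies below any one of them on average.

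Describing the PK of bedaquiline, delamanid and moxifloxacin with their main metabolites is the secondary PK objective. If section 9 is followed as written, the study report would show under the name Cmin a quantity other than the protocol's timed endpoint, and the gap would differ by analyte. Where the trough sample is missing, section 9 would still return a Cmin from another time, possibly above the true trough, and the gap in the data would not show.

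**Working it through.** **Count and direction.** The listed times are 0, 1, 2, 4, 8, 12 and 24 h: 1 predose + 6 post-dose = 7, as the protocol states. The timed trough is one of the six, so min(six values) ≤ trough whenever the trough is measured. This needs no assumption.

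**Inputs from the documents.** Bedaquiline half-life 132 days, M2 112 days, bedaquiline Tmax 4–6 h (protocol 7.1.2); delamanid half-life 30–38 h, its main metabolites 150–600 h, Tmax 4 h (protocol 7.2.3); delamanid taken mornings and evenings (protocol Table 1).

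**Assumptions not in the documents.** Independent log-normal within-profile noise, CV 5% to 20%; one-compartment shape for parents; delamanid ka 0.6/h and lag 0.5 h; metabolites formed at a constant rate from the first dose; moxifloxacin half-life 8–14 h and Tmax 2–4 h; an effective bedaquiline half-life varied from 24 h to 132 days. Bias is the geometric mean of the section 9 value divided by that of the timed value, minus 1.

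**Flat profile.** The expected minimum of six standard normals is −1.267. With s = √ln(1 + CV²), bias = exp(−1.267 s) − 1. CV 5%: s = 0.0500, −6.1%. CV 10%: s = 0.0998, −11.9%. CV 15%: s = 0.1492, −17.2%. CV 20%: s = 0.1980, −22.2%.

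**M2 without noise.** Level ∝ 1 − exp(−kt), with k = ln 2/(112 × 24) = 0.000258 per h. The day-14 dose is at 13 × 24 = 312 h. At 313 h (the 1 h sample) the level is 0.0775; at 336 h (the 24 h sample) it is 0.0830. The ratio is 0.934, so section 9 reads 6.6% low with no noise at all.

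**Delamanid.** Steady-state superposition of 12-hourly doses. The 12 h and 24 h samples come out equal to within 0.1%, because each is about 12 h after a dose. Both therefore fit the SAP 5.3 wording, and two benchmarks are shown.

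| Analyte and benchmark | CV 5% | CV 20% |
|---|---|---|
| Flat profile | −6.1% | −22.2% |
| M2 against 24 h, still accumulating | −10.9% | −25.8% |
| Delamanid against 12 h sample (half-life 30 to 38 h) | −3.2 to −3.4% | −17.6 to −18.4% |
| Delamanid against the lower of 12 h and 24 h | −0.4 to −0.6% | −7.9 to −8.8% |
| DM-6705 against 12 h, if the rule were extended to it (half-life 150 to 600 h) | −6.7 to −7.5% | −22.7 to −23.0% |
| Bedaquiline, half-life 132 days | −6.1% | −22.1% |
| Bedaquiline, effective half-life 72 h | −0.3% | −13.1% |
| Bedaquiline, effective half-life 24 h | 0.0% | −3.1% |
| Moxifloxacin, no absorption lag | 0.0% | 0.0 to −0.2% |

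DM-6705 without noise is 1.5% to 2.8% low against the 12 h sample. Adding a 1 h absorption lag moves bedaquiline to between −4% and −24% across half-lives. For moxifloxacin a 1 h lag gives −6.4% to −13.4%, because the 1 h sample is then itself at about trough; without it the 24 h sample is almost always the lowest.

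**The case against.** The strongest reply is that the two definitions are closer than they look. SAP 5.3 reads "The minimum observed plasma concentration (Cmin) at day 14 (24 hours following the last dose for QD and 12 hours following the last dose for" twice-daily intake, so the endpoint is itself called a minimum observed concentration, and the bracket could be taken as saying where that minimum is expected. This softens the conflict but does not remove it. The bracket names a time, section 9 names none, and a programmer following section 9 would search all six samples.

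The second reply concerns delamanid. SAP 5.3 says 12 hours after the last dose, not the 12 h sample, and the 24 h sample is also about 12 h after the evening dose. This stands: more than half of the gap against the 12 h sample comes from counting a value that SAP 5.3 also allows.

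The third is that little depends on it. The outputs are descriptive statistics by dose group with no test. The same rule applies in all arms, so between-arm ratios are largely preserved if noise is similar, and the planned concentration-time graphs will show the 12 h and 24 h levels. This stands too, and keeps the point minor.

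A reader might go further and infer that Cmin is biased low for every companion drug, that the M2 gap is purely a matter of assay noise, or that the primary analysis is affected. The documents support none of these. Moxifloxacin falls steeply enough for the rules to agree unless absorption is delayed. The M2 gap in this model exists without noise. SAP 10.2 uses delpazolid Cmin derived from the population PK model, which section 9 does not touch.

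**Conclusion.** The point holds as an inconsistency within the SAP and between SAP section 9 and the protocol. The direction is certain when the timed sample is measured: equal or lower. The size is not known from the documents. Under the stated assumptions it is largest for flat or still-accumulating analytes, where M2 could be 11% to 26% low. It is moderate to small for delamanid, depending on which of two valid troughs is the benchmark. It is undetermined for bedaquiline, and essentially nil for moxifloxacin without an absorption lag. The M2 figure rests on the 112-day half-life and constant formation; a shorter effective half-life would shrink the part that does not come from noise. The reach is limited to descriptive secondary PK summaries, so this is a minor correction, best made before the companion-drug analysis is run.

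**What to change.** In SAP section 9, replace the Cmin definition with a timed one:

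- bedaquiline, M2 and moxifloxacin: the measured 24 h concentration;
- delamanid and DM-6705: the measured 12 h concentration, drawn before the evening dose, with a statement that this is the chosen one of two samples that fit SAP 5.3;
- missing if that sample is missing, with no substitution from another time;
- if the lowest observed value is also wanted, report it under a different name.

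Add DM-6705 to the analytes in section 9 so that it matches SAP 5.3. Protocol 11.5 does not state whether the 12 h draw precedes the evening dose, so check this against the recorded sampling and dosing times.

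The cost is a few lines of SAP text and one programming change. No new samples or assays are needed for the timed definition.
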